6.2.3.4 Conventional Intubation, surfactant administration and brief ventilation

As standard control treatment, neonates spontaneously breathing and stabilized on NIV will receive surfactant via ETT using an approved method of administration, connecting the syringe filled with poractant alfa suspension to:

- a 5-French end-hole catheter inserted into the ETT
or
- the proximal end of the secondary lumen of a dual lumen ETT.

The standard ETT has markings along the side to help identifying the correct distance from the tip of the tube.

Following direct laryngoscopy, the ETT will be inserted through the vocal cords into the trachea to the desired depth. The laryngoscope will be then carefully removed. The correct ETT position into the trachea will be confirmed by the visualization of tip depth markings and by the tip-to-lip measurement. The tube position could be checked by auscultation of the chest to ensure equal aeration of both lungs, observation of chest movement synchronous with positive pressure inflation, enhancement of vital signs, absence of stomach distension while ventilation, and where possible, with the measurement of end tidal CO₂ by colorimetric system on the ETT. Once the tube position is confirmed, the ETT will be secured with adhesive tape or other ways according to the NICU policy.

After administration, manual ventilation can be continued, or the neonate can be connected to the ventilator, or the neonate can be immediately extubated and placed again on NIV. Do not suction airways for 1 hour after surfactant instillation unless signs of significant airway obstruction occur.

If connected to the ventilator, extubation should be performed within one hour after surfactant administration and then the neonate placed again on NIV.

Details of the procedure as well as neonate's vital signs and any occurring adverse event will be recorded according to the time points of the protocol by the team member assisting or observing the procedure.

6.2.3.5 Need for resuscitation during surfactant administration

In both arms of the study, if a life-threatening event requiring resuscitation occurs during poractant alfa administration, the procedure of surfactant administration will be stopped and resuscitation provided starting from supplying Positive Pressure Ventilation (PPV) and following step-by-step the American Guidelines for Neonatal Resuscitation [[24,25](#)].

6.2.3.6 Additional surfactant treatment

Up to two repeated doses could be administered at 100 mg/kg.

A second surfactant dose (poractant alfa 100 mg/kg) will be administered using the same technique as the first dose administration in case of lack of efficacy, or clinical deterioration,

as per randomization criteria ($FiO_2 \geq 0.30$ to maintain preductal oxygen saturation (SpO_2) in the target range 88–95%), within approximately 12 hours from the initial dose.

After the first and the second surfactant administration, neonates could receive a third surfactant dose (poractant alfa 100 mg/kg). If a third dose is administered, it will be provided through a standard technique. Neonates could be intubated (LISA group) or re-intubated (control group) for MV at neonatologist's discretion, if one or more of the below detailed conditions for MV in section 6.2.3.7 are satisfied.

6.2.3.7 Intubation and extubation criteria

Intubation for mechanical ventilation and further surfactant doses could happen if one or more of the following criteria are satisfied:

- $FiO_2 \geq 0.45$ to maintain preductal SpO_2 of 88-95% for at least 30 minutes, unless rapid clinical deterioration occurs;
- Significant apnea (more than four episodes of apnea/hour or more than two episodes of apnea/hour if ventilation with bag and mask was required);
- Respiratory acidosis ($pCO_2 > 65$ mmHg/8.5 kPa and $pH < 7.20$ identified by either arterial or capillary blood gas monitoring).

These criteria will be applied during the first 3 days of life (72 hours).

After the first 3 days of life, intubation and mechanical ventilation can happen as per Investigator's clinical judgement.

FiO_2 and SpO_2 values should be collected at time of decision for intubation and recorded in eCRF as well as the criterion for intubation.

Criteria for termination of Mechanical Ventilation and Extubation are defined as follows:

- Clinical improvement, e.g. presence of a good respiratory drive;
- Ability to wean FiO_2 , e.g. $FiO_2 < 0.30$ to maintain SpO_2 between 88 and 95%.
- Ability to wean ventilatory pressures, e.g. $MAP \leq 7$ in conventional ventilation or $MAP \leq 8$ in HFOV;
- Normalization of blood gases' values, e.g. $pCO_2 < 65$ mmHg and $pH \geq 7.20$.

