---------------------------	--

	
target range of 88 and 95%;
 
 • Ability to wean ventilatory pressures, e.g. MAP ≤ 7 in conventional ventilation or MAP ≤ 8 in HFOV; • Normalization of blood gases' values, e.g. pCO₂ <65 mmHg and pH ≥ 7.20.
Test product dose/route/regimen	
Poractant alfa 200 mg/kg or 100 mg/kg (for additional doses, if needed) is a sterile suspension in 3.0 mL glass vials with a total concentration of 80 mg/mL for intratracheal administration. This is a standard natural surfactant prepared from porcine lungs and containing almost exclusively polar lipids, in particular phosphatidylcholine (about 70% of the total phospholipid content), and about 1% of specific low molecular weight hydrophobic proteins SP-B and SP-C.
 
LISA-delivery of poractant alfa to the lung will be done via brief insertion of a thin catheter (CHF 6440) through the mouth into the trachea while the subject is being supported with NIV (CPAP, NIPPV, BiPAP). The thin catheter will be provided by the Sponsor. CHF 6440 is a sterile, single-use catheter. It has a working length of 130.0 mm, presents a 1.7 mm Outer Diameter (corresponding to a 5 French OD), with a 1.1 mm Internal Diameter (corresponding to 3.5 French ID) through which the surfactant is delivered. The hole at the distal edge has a diameter of 0.8 mm.
 
Printed depth markings on the outer surface of the shaft provide visual guide to the depth of device insertion during clinical procedure.
 
The neonate will be placed supine with the head in the neutral position prior to the onset of the LISA procedure. Following direct laryngoscopy, the catheter will be introduced orally and inserted through the vocal cords into the trachea, the laryngoscope will be carefully removed while the position of the catheter is secured by the fingers of the neonatologist/investigator who will finally close the neonate's mouth. Surfactant will be slowly administered over 0.5-3 minutes with careful observation of the neonate's continuous spontaneous breathing. Before removing the LISA catheter, it should be fully cleared of surfactant with some additional air. After completion of surfactant administration, the ventilatory support may require transient adjustments. Airways suction should not be performed for 1 hour after surfactant instillation, unless signs of significant airway obstruction occur.

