3. STUDY DESIGN

This is an open-label, multicenter, randomized and controlled study. Approximately 25 investigational sites will be involved in US. Neonates will be evaluated according to the selection criteria and then randomized to surfactant treatment via LISA or standard administration procedure ([Table 1](#)). The enrollment will be staggered: the gestational age will be restricted to 27⁺⁰ weeks up to 28⁺⁶ completed weeks until safety evaluation by ISMB is performed for the first 15 neonates. Provided no safety concerns are raised, the enrollment will then be extended to the whole population (i.e. 25⁺⁰ weeks up to 28⁺⁶ completed weeks).

[figure not shown]
Enrolled neonates will be evaluated:

- until discharge,
- until 40 weeks PMA (if still in hospital),
- if discharge occurs before 36 weeks, the last evaluation will be at 36 weeks PMA.

This period represents the main phase of the trial.

Their final assessment of development will be at 24-month corrected age as a separate stand-alone visit. This 24-month clinical assessment will be analyzed and evaluated separately from the initial part of the study and will be object of an addendum to the initial core clinical study report.

Table 1: TIMETABLE

End of the trial

The end of the trial will correspond to the last evaluation of the last neonate from the recruiting site or from the continuing care site in case the treated baby was transferred from the original recruiting site. The last evaluation could be:

- the date of the assessment for BPD diagnosis (i.e. 36 weeks PMA) if the patient is discharged home before 36 weeks PMA,
- discharge home (if discharged between 36 weeks and 40 weeks PMA), or
- 40 weeks PMA (if still in hospital).

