8. EFFICACY ASSESSMENTS

The following variables will be used to describe the efficacy of the two procedures:

- Percentage of neonates needing invasive mechanical ventilation (MV) in the first 72 hours of life, 28 days PNA and within 36 weeks PMA defined as follows:

ETT group

- neonates not extubated within 1 hour from initial surfactant administration and receiving MV for more than 1 hour;
- neonates extubated and re-intubated to receive MV of any duration.

LISA group

- neonates intubated to receive MV of any duration,
 - Duration of invasive ventilation (hours) in the first 72 hours of life, 28 days PNA and within 36 weeks PMA;
 - Percentage of neonates needing any intubation procedure, outside the initial surfactant administration period, in the first 72 hours of life, in the first 28 days PNA and within 36 weeks PMA;
 - SpO₂ at time 0 (study treatment administration), 5, 15, 30 minutes, at 1, 6, 12, 24, 48, 72 and 120 hours post treatment; additionally, at 28 days PNA and at 36 weeks PMA for neonates still receiving any form of respiratory support;
 - FiO₂ at time 0 (study treatment administration), 5, 15, 30 minutes, at 1, 6, 12, 24, 48, 72 and 120 hours post treatment; additionally, at 28 days PNA and at 36 weeks PMA for neonates still receiving any form of respiratory

support;

- SpO₂/FiO₂ at time 0 (study treatment administration), 5, 15, 30 minutes, at 1, 6, 12, 24, 48, 72 and 120 hours post treatment; additionally, at 28 days PNA and at 36 weeks PMA for neonates still receiving any form of respiratory support;
- Percentage of neonates needing additional surfactant doses and number of surfactant doses;
- Duration of oxygen alone supplementation (days) and any non-invasive ventilation during the study (days);
- Blood gas analysis, specifically acid-base balance parameters (i.e. pH, pCO₂, pO₂, HCO₃, BE, lactate) pre-surfactant administration (when applicable), at 1 hour, 6 hours, 24, 48 and 72 hours after study treatment.

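### The pCO2 cut-off for intubation carries a wrong unit conversion: 65 mmHg is 8.7 kPa, not 8.5 kPa

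*Protocol*

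**What the plan says.** Section 6.2.3.7 lists three conditions, any one of which may lead to intubation for mechanical ventilation and further surfactant during the first 72 hours of life. The third is "Respiratory acidosis ($pCO_2 > 65$ mmHg/8.5 kPa and $pH < 7.20$ identified by either arterial or capillary blood gas monitoring". The Protocol Outline (Treatment duration) repeats the criterion with the same two pCO2 figures.

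The matching criterion for ending ventilation is in mmHg only. In Section 6.2.3.7 it reads "Normalization of blood gases' values, e.g. $pCO_2 < 65$ mmHg and $pH \geq 7.20", and the Outline has "e.g. pCO₂ <65 mmHg and pH ≥ 7.20". Nothing elsewhere in the protocol corrects or explains the kPa figure.

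Section 6.2.3.7 also requires the criterion that prompted intubation to be recorded in the eCRF.

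**The concern.** The slash presents 65 mmHg and 8.5 kPa as one threshold in two units. They are not equal, so the text contains two cut-offs. Between them, whether a neonate met the criterion depends on the unit used.

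The figure stands in operative text as a decision threshold for intubating preterm neonates, and the criterion met becomes a recorded data item. Need for invasive ventilation in the first 72 hours is one of the efficacy variables, so it is worth asking whether the discrepancy could reach that endpoint.

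**Working it through.** **Inputs.** The pCO2 threshold is 65 mmHg with a stated equivalent of 8.5 kPa (Section 6.2.3.7 and the Protocol Outline). The conversion factor is the standard one: 1 mmHg = 101.325/760 = 0.133322 kPa.

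**Trying to reproduce 8.5 kPa.**
- 65 × 0.133322 = 8.666 kPa
- 65 × 0.1333 = 8.664 kPa
- 65 / 7.5 = 8.667 kPa

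All three round to 8.7. Only a factor cut to two decimals comes near the printed figure: 65 × 0.13 = 8.45, which rounds up to 8.5. That may be how the slip arose, but the factor is too coarse for a one-decimal result.

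**In reverse.** 8.5 / 0.133322 = 63.76 mmHg.

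**Size of the gap.** 8.666 − 8.5 = 0.166 kPa. Relative to the correct value this is 0.166 / 8.666 = 1.9%. In mmHg it is 65 − 63.76 = 1.24.

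**Can rounding explain it?**

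| Printed value | Values that round to it | In the other unit |
|---|---|---|
| 65 mmHg | 64.5 to 65.5 mmHg | 8.60 to 8.73 kPa |
| 8.5 kPa | 8.45 to 8.55 kPa | 63.4 to 64.1 mmHg |

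The ranges do not overlap in either unit, so no single threshold rounds to both figures.

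**Which readings are affected (with pH below 7.20).**
- Whole mmHg: 64 mmHg = 8.533 kPa and 65 mmHg = 8.666 kPa. Both exceed 8.5 kPa and neither exceeds 65 mmHg. A reading of 63 mmHg (8.399 kPa) meets neither form.
- kPa to one decimal: a displayed 8.6 stands for 8.55 to 8.65 kPa, which is 64.1 to 64.9 mmHg. It passes the kPa form although every value it can stand for is below 65 mmHg. A displayed 8.5 does not exceed 8.5, and a displayed 8.7 straddles 65 mmHg.

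**Which figure is wrong?** The mmHg value comes first, and the extubation criterion uses 65 mmHg alone in both places. That points to 65 mmHg as the intended cut-off.

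**Does it reach the endpoint?** Section 8 classifies need for invasive ventilation by the ventilation received. In the LISA group, for example, it counts "neonates intubated to receive MV of any duration". There is no pCO2 term, so any influence could come only through a clinician's decision to intubate.

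**The case against.** The case for leaving it alone rests on consequence, because the arithmetic is not in dispute.

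- **The kPa figure may never be used.** The protocol states that "Approximately 25 investigational sites will be involved in US", and the mmHg value is printed first. A site whose analyser reads mmHg would apply 65 mmHg and ignore the conversion. The slip matters only with a kPa readout, and then essentially for a displayed 8.6. This is a fair inference, but the protocol names no reporting unit.
- **The criterion does not bind treatment.** It permits intubation at the neonatologist's discretion, is one of three alternatives, needs a low pH as well, and lapses after 72 hours. A neonate in the narrow band may qualify on FiO2 or apnea anyway. This stands.
- **No analysis in the protocol depends on it.** Section 12.3.4 compares ventilation received and summarises blood gases as measured. It plans nothing by intubation criterion, and the eCRF entry has no stated analytical use. Section 12.1 defines no primary efficacy endpoint and gives no power calculation. This also stands.
- **The extubation value is only an example.** It is introduced as an illustration, so it supports 65 mmHg as the intended figure without proving it. This is correct, and it is why the conclusion about intent is put as likely.

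These points keep the matter at the level of a minor correction. None of them makes 8.5 kPa the equivalent of 65 mmHg.

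**Conclusion.** The concern holds. The kPa equivalent is wrong in both places by 0.17 kPa (1.9%, about 1.2 mmHg), beyond anything rounding at the printed precision can produce. The error makes the kPa form slightly easier to meet than the mmHg form.

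The effect on the trial is close to nil, and exactly nil if all sites read mmHg, which is an assumption. The wording is the same for both arms, so it gives no ground for claiming bias. Sample size and analysis methods are untouched. It is a minor point, worth correcting because a clinical cut-off should have one value.

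**What to change.** In Section 6.2.3.7 and in the Treatment duration entry of the Protocol Outline, either give the threshold as pCO2 > 65 mmHg (8.7 kPa) or delete the kPa figure.

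Deletion is slightly cleaner for a US-only study. It matches the extubation criterion, which has no kPa value, and it leaves no rounding residue (8.7 / 0.133322 = 65.26 mmHg, still 0.26 mmHg from the cut-off).

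The cost is one figure in two places, with no effect on design or analysis. It can go into the next amendment.

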6.2.4 Subject Training

Not Applicable.

6.3 Packaging

Chiesi Farmaceutici S.p.A. will supply the study medication for both groups as well as the thin catheter (CHF 6440) for the administration in the relevant LISA treatment group.

The study medication kit is composed of a single glass vials of 3 ml of Poractant alfa for initial dosing or possible re-dosing; the vial will be packed in an outer box and will be provided to

the investigational sites. Each vial is for single use only. Any need for dosing and re-dosing will require a vial to be issued via IRT (see Section [6.6](#)).

CHF 6440 catheters will be packed and provided separately.

6.3.1 Primary packaging

Poractant alfa:

Labeled glass vial containing 3 ml of Poractant alfa at a concentration of 80 mg/ml for respectively initial dosing and possible re-dosing.

CHF 6440 catheters:

A sterile labeled tyvek pouch containing CHF 6440 catheter.

6.3.2 Secondary packaging

Poractant alfa:

A holder containing one labelled glass vial containing 3 ml of Poractant alfa.

CHF 6440 catheter:

A labeled carton containing a tyvek pouch .

6.3.3 Tertiary packaging

Not applicable.

6.4 Labeling

The supplies (Poractant alfa and CHF 6440 catheters, in primary and secondary packaging) will be labeled in English and according to US law and FDA regulatory requirements in compliance with Annex 13 of Volume 4 of the GMPs and in compliance with 21 CFR 312.6 “Labelling of an Investigational New Drug”, for US Trials.

The tear-off sticker from the vial box and the tear off sticker from the catheter carton will be applied in the appropriate section of the surfactant accountability log.

6.5 Treatment allocation

A balanced block randomization scheme stratified by investigational site and gestational age group (i.e. from 25⁺⁰ to 26⁺⁶ weeks and from 27⁺⁰ to 28⁺⁶ weeks) will be prepared via a computerized system. Once the neonate’s eligibility to take part in the study is confirmed, neonates will be centrally assigned to one of the two treatment arms (LISA/Poractant alfa or ETT/Poractant alfa) through an IRT system (Interactive Response Technology, combination of voice and web response system and also referred as IVRS/IWRS). Enrollment will be staggered: the gestational age will be restricted to 27⁺⁰ to 28⁺⁶ weeks for at least the first 15 randomized neonates. After ISMB evaluation of safety data from the first 15 neonates, provided no safety concerns are raised, the enrolment will be extended to the whole population (25⁺⁰ to 26⁺⁶ weeks and from 27⁺⁰ to 28⁺⁶ weeks).

The IRT will allocate the subject to a certain treatment group using a list-based randomization algorithm and assign the unique screening number of eight digits: the country will be the first three digits (according to ISO 3166 Numeric Country Code), the investigational site number will be the second two digits and the following three digits will be the progressive numbering of the subject within each site (e.g. for the first USA site the screening numbers will be 84001001, 84001002 etc.). The IRT will also generate a confirmation after every IRT transaction is performed.

The Investigator will call the IRT on admission to receive the subject screening number and randomize the subject and obtain the medication (Poractant alfa) kit numbers. Detailed instructions for use of IRT will be provided to the site.

In the LISA group, the relevant catheter provided by the Sponsor (CHF 6440) will be dispensed and used for administration. In the control group, the endotracheal tubes available at the investigational sites for clinical practice will be used for administration.

The LISA catheter (CHF 6440) will be dispensed by the IRT system.

6.6 Treatment Code

The study medication (Poractant alfa) will be packaged and uniquely numbered. The IRT will be used to assign both initial and subsequent kits in order to have an inventory control and subject dosing tracking. The IRT will also maintain quantities, kit numbers, drug types, batch/code numbers, expiration dates and do not dispense after these dates. The IRT will monitor inventory levels at all sites and manage the study drug re-supply.

6.7 Treatment compliance

The actual volume of poractant alfa administered will be entered in eCRF. The evaluation of compliance will be done based on the actual volume administered in relation to the neonates' weight using the following formula:

$\text{Volume administered} / \text{Volume scheduled} * 100\% = \% \text{ of administered volume}$

The volume scheduled will be calculated on the basis of neonates' weight as 2.5ml x birth weight (kg) for the first dose and as 1.25 ml x birth weight (kg) for following doses.

6.8 Drug and Device Storage

The Pharmacist/Investigator will be responsible for the safe storage of all medications and catheters assigned to this study, in a secure place with restricted access, and maintained within the appropriate ranges of temperature.

Poractant alfa will have to be stored between 2° and 8°C (36° to 46°F), protected from light, until the moment of use.

CHF 6440 catheter does not require any special storage condition. Keep in a cool dry place.

Please refer to CTS Instructions for Use.

6.9 Drug Accountability

The Investigator or pharmacist is responsible for the management of all the study treatments and thin catheters CHF 6440 to be used for the study. Study treatments should be stored in a locked, secure storage facility with access limited to those individuals authorized to dispense the study drugs.

An inventory will be maintained by the Investigator or pharmacist (or other nominated individual), to include a signed account of all the study treatment(s) and LISA catheters received and used for each subject. The actual volume of instilled study treatment will be reported in the relevant section of the eCRF.

At the conclusion or termination of the study, the Investigator or the pharmacist shall conduct and document a final drug supply (used and unused) inventory. An explanation should be given for any discrepancies.

No surfactant material or catheters for this trial are to be used for any other purpose.

In addition, a signed account shall be kept of all study treatments administered to each subject.

All the study treatments supplied, used or unused, will be returned for destruction to the designated Clinical Trial Supply (CTS) vendor/depot under Sponsor's responsibility or destroyed directly by the Pharmacy of the involved investigational site upon provision of destruction certificate and documentation assuring the occurred destruction according to standard procedures and filed both at investigator's site file and at Sponsor/CRO trial master file.

6.10 Provision of additional care

At study completion, it is the Investigator's responsibility to prescribe the more appropriate treatment for the subject.

7. STUDY PLAN

7.1 Study Schedule

This study will include the following periods and visits:

Periods:

- Pre-randomization period: on admission to the study prior to study treatment;
- Day 1: randomization, before start of study procedure, treatment administration up to end of surfactant administration (T0); up to 24 hours after receiving study treatment (5, 15, 30 min, 1, 6, 12, 24 hours);
- Day 2: from 24 hours to 48 hours post treatment;
- Day 3: from 48 hours to 72 hours post treatment;

- Day 5: from 96 hours to 120 hours post treatment.

Follow-up visits:

- 28 days Post-Natal Age (PNA);
- 36 weeks Post-Menstrual Age (PMA);
- Discharge home or 40 weeks PMA, whichever comes first;
- 24 months (± 3 months) corrected age visit.

Details are reported in the following sections and summarized in the following flowchart ([Table 2](#)):

The following time deviations from theoretical post-dose times will be allowed:

Table 3: ALLOWED TIME DEVIATIONS

Post-dose time assessments	Allowed deviations
5, 15 minutes	+ 1 minute
30 minutes	+ 5 minutes
1 hour	+ 10 minutes
6, 12 and 24 hours	+ 30 minutes
48, 72, and 120 hours	+ 2 hours
28 days PNA	+ 2 days
36 wks PMA	+ 4 days
40 wks PMA (if still in hospital)	+ 2 days
24 months clinical assessment	+ 3 months

